A study psychiatrist or medically qualified designate will release the subject at the conclusion of the testing period at the end of the visit. A trained research assistant along with a research nurse will be present during the entire infusion and monitoring period. The psychiatry research staff member will administer rating scales. All side effects and vital parameters will be recorded during the infusion and 2 hours following. Any abnormal, clinically significant vital signs will be recorded as adverse events.

Discharge Procedure: Gross motor and cognitive function, ataxia, reflexes/clonus will be evaluated and documented by a study psychiatrist or medically qualified designate prior

to discharge. Before being discharged patients should be awake and alert, feeling well, with no nausea, vertigo, or dizziness. There should be no significant change in vital signs from prior to infusion. They will be given a small meal before discharge.

Patients will be instructed not to drive. If necessary, the study nurse will release them to the care of an adult family member or caregiver, who will accompany the patient home.

Reliability Training

All physicians/raters involved in the assessment of study subjects will use standardized clinician-rated measures such as the SCID I/P, the PANSS, and CGI-S. Training in the use of these instruments occurs through videotaped and live interviews of mock patients. Both intra-individual and inter-individual reliability measures will be reported.

Patient Adherence to Protocol

Every effort will be made to encourage patients to comply with the procedures and the assessments involved in study. Patients will be compensated for their time at each visit, at a rate determined appropriate by each individual IRB (estimated compensation: \$20.00/hour). This level of subject compensation, while non-coercive, facilitates adherence to assessments and procedures that require weekly visits.

Subjects and clinicians will be asked to guess which arm of the study the subjects were in at the end of the study to assess if blinding was successful.

Evaluation of Adverse Events (AEs)

Definition

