AEs will be captured from the first study-related procedure through to the completion of the protocol defined safety surveillance period. For the purposes of this study, the period of observation for collection of AEs extends from the time the subject gives informed consent until the final visit.

Surgical procedures, planned before enrollment of the subject in the study, are not considered AEs if the condition was known before study inclusion. In this case the medical condition should be reported in the subject's medical history. Intermittent adverse events will not be reported as multiple adverse events. The definition of an intermittent adverse event is "a recurring event of consistent severity, frequency, and causality."

Severity

Each AE is to be documented with reference to severity. Changes in severity of AEs and resolution dates should be documented as separate events. Any event that ameliorates over more than one assessment time point may be considered for listing as a single event at the highest severity.

Table 2. Definition of Intensity of Adverse Events

Intensity	Definition
Mild	Causes transient or mild discomfort; no limitation of usual activities; no medical intervention required.
Moderate	Causes mild to moderate limitation in activity; some limitation of usual activities; no or minimal medical intervention or therapy is required.
Severe	Causes marked limitation in activity; some assistance is usually required; medical intervention or therapy is required; hospitalization is probable.

The term “severe” is often used to describe the intensity (severity) of a specific event (as in mild, moderate, or severe); the event itself, however, may be of relatively minor medical significance (such as a severe headache). This is not the same as “serious,” which is based on subject/event outcome or action criteria usually associated with events that pose a threat to a subject’s life or functioning. Seriousness (not severity) serves as a guide for defining regulatory reporting obligations.

Relationship

The PI or a medically qualified Sub-Investigator, trained on this study protocol, listed on the 1572 or equivalent document and on the delegation of authority form, is responsible for determining the adverse event relationship to the investigational product.

The following categories will be used to define the relationship of an AE to the administration of the IMP:

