- Not Related: Data are available to identify a clear alternative cause for the AE other than the investigational product.
- Related: The cause of the AE is related to the investigational product and cannot be reasonably explained by other factors (e.g., the subject’s clinical state, concomitant therapy, and/or other interventions).

Expectedness

An unexpected AE is any AE, the nature and severity of which is not consistent with the applicable product information (e.g., Package Insert of product characteristics for an approved product).

Clinical Significance

The PI or a medically qualified Sub-Investigator, trained on this study protocol who is listed on the 1572 or equivalent document and on the delegation of authority form, is responsible for determining the clinical significance of abnormal results (e.g., labs, ECG results) for the subject.

Clinical Laboratory Adverse Events

Changes in laboratory values or vital signs, or other safety parameters (e.g., ECG, study assessments) as noted in the protocol, are a subset of AEs and are reportable only if considered to be clinically significant by the PI or medically qualified Sub-Investigator.

Screening assessment exams are differentiated from adverse events/symptoms that are incurred post informed consent. Pre-dose abnormal results without clinical symptoms will not be reported as adverse events.

Pregnancy

If a subject (or subject's partner) becomes pregnant during the study, it must be reported in within 24 hours of the time the investigator becomes aware of the event and in accordance with the procedures described on the Pregnancy Report Form. Pregnancy in itself is not regarded as an AE unless there is a suspicion that a study drug may have interfered with the effectiveness of a contraceptive medication. Any pregnancy that occurs from Day 1 to 30 days following the last dose given will be followed for Serious Adverse Events (SAEs).

Evaluation of Serious Adverse Events (SAEs)

Definition

An SAE is defined by federal regulation as any AE occurring at any dose that results in any of the following outcomes:

- Death
- Life-threatening event
- Hospitalization or prolongation of hospitalization
- Persistent or significant disability/incapacity
- Congenital anomaly/birth defect

Reporting Serious Adverse Events

All SAEs will be reported to MGH-CTNI by the PI through telephone or email within 24 hours of discovery, using the form provided by the CTNI.

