## **Safety Analyses**

### Adverse Events

Adverse events will be coded using MedDRA. Treatment Emergent AE's (TEAE) are defined as events with an onset on or after the first randomized treatment. TEAEs will be summarized by treatment group and by stage of the study, System Organ Class, and preferred term. The following TEAE summaries will be provided:

- TEAEs by severity grade
- TEAEs by relationship to study treatment.

In addition, separate summaries of serious adverse events, and adverse events resulting in discontinuation of study treatment will be presented.

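### The intermittent adverse event rule has no boundary at the second infusion, so a reaction seen on placebo and again on nitroprusside can be recorded once, under placebo only

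*Protocol*

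**What the plan says.** **Recording.** Protocol section H, Evaluation of Adverse Events, Timing: "Intermittent adverse events will not be reported as multiple adverse events". An intermittent event is defined as "a recurring event of consistent severity, frequency, and causality". The window is continuous: "the period of observation for collection of AEs extends from the time the subject gives informed consent until the final visit". Nothing ties the rule to a phase or an infusion, and consistent is not defined.

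The same section, under Performing Adverse Events Assessments and again under Severity, says: "Changes in severity of AEs and resolution dates should be documented as separate events".

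Causality (section H, Relationship) has two categories, Related and Not Related. Related means: "The cause of the AE is related to the investigational product and cannot be reasonably explained by other factors".

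**Analysis.** In the SAP (Safety Analyses, Adverse Events), TEAEs are "defined as events with an onset on or after the first randomized treatment", and "TEAEs will be summarized by treatment group and by stage of the study, System Organ Class, and preferred term". Protocol section M has the same text. Protocol section H (Treatment-Emergent Adverse Events) is wider: it also counts an event present before treatment that then increases in frequency or severity.

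**Design.** Protocol section F has 20 subjects in each of three sequences (drug-drug, placebo-drug, placebo-placebo), with infusions on Day 0 and Day 14. No sequence goes from drug to placebo.

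**The concern.** Every subject is infused twice, 14 days apart, and a third of them change from placebo to nitroprusside. A merging rule that ignores the second infusion fits poorly with a table that assigns each event to a treatment and stage by its onset date. Neither document says which treatment or stage owns an event that occurs after both infusions.

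The sentence on resolution dates does not settle the matter. A recurring event normally resolves between episodes. If a different resolution date always makes a new event, the intermittent rule has almost nothing left to act on. If the intermittent rule prevails, the second episode has no record. Each site can defend its own reading.

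Safety and tolerability is the only secondary objective, and TEAE incidence heads the list of safety assessments. An episode merged at the site cannot be restored by the analyst, because the second onset date never reaches the database as an adverse event.

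**Working it through.** **Plan's own figure.** There is none to reproduce: neither document states an expected adverse event rate. The only design calculation is the power for the PANSS endpoint, which does not bear on this point.

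**Step 1. Each sequence, same mild reaction after both infusions, merged into the first onset**

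| Sequence | Record kept | What is lost |
|---|---|---|
| placebo-drug | Phase 1 onset, placebo | the subject's nitroprusside event |
| drug-drug | Phase 1 onset, nitroprusside | Stage 2 entry and one event; the subject still counts under nitroprusside |
| placebo-placebo | Phase 1 onset, placebo | Stage 2 entry and one event; the subject still counts under placebo |

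The placebo episode in the first row belonged under placebo anyway, so pooled placebo incidence does not change. Because no sequence runs from drug to placebo, merging can only lower pooled nitroprusside incidence at subject level.

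**Step 2. Size for one preferred term.** Inputs from the documents: 20 subjects per sequence, hence 40 exposed to nitroprusside. Assumptions: all subjects receive both infusions; per-infusion probability pd = 0.30 on drug and pp = 0.10 on placebo; a share s of recurrences is merged; the two episodes are independent or have latent (bivariate normal) correlation 0.5 or 0.8.

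Let B be the probability of the event after both infusions.

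- Pooled nitroprusside loss = 20 × s × B(placebo-drug) / 40.
- Stage 2 recorded rate in a sequence = Stage 2 true rate − s × B. The nitroprusside column averages drug-drug and placebo-drug.

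Under independence with s = 1, B(placebo-drug) = 0.10 × 0.30 = 0.03. The loss is 20 × 0.03 = 0.6 subjects, and 0.6/40 = 1.5 points. Pooled incidence with every episode attributed to its own infusion is [20 × (1 − 0.7²) + 20 × 0.3]/40 = 16.2/40 = 40.5%. Recorded, it is 15.6/40 = 39.0%.

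Stage 2 nitroprusside: drug-drug 0.30 − 0.09 = 0.21, placebo-drug 0.30 − 0.03 = 0.27, average 0.24. Stage 2 placebo: 0.10 − 0.01 = 0.09.

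| All merged (s = 1) | Independent | Corr. 0.5 | Corr. 0.8 |
|---|---|---|---|
| Placebo-drug subjects lost, of 20 | 0.6 | 1.3 | 1.8 |
| Pooled nitroprusside, true → recorded | 40.5% → 39.0% | 37% → 34% | 34% → 30% |
| Pooled loss, points | 1.5 | 3.3 | 4.5 |
| Stage 2 nitroprusside (true 30%) | 24% | 19% | 15% |
| Stage 2 placebo (true 10%) | 9.0% | 6.8% | 4.4% |
| Stage 2 difference (true 20 points) | 15 | 12 | 10.5 |

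With half merged (s = 0.5), Stage 2 nitroprusside reads 27%, 24% and 22%. With none merged, every loss is zero.

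**Step 3. Other assumed rates** (independent, all merged). The pooled loss is 20 × pp × pd / 40:

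- 5% placebo, 20% drug: 0.5 points
- 20% placebo, 40% drug: 4.0 points
- 30% placebo, 50% drug: 7.5 points

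**The case against.** The strongest reply is that the protocol already separates the two episodes. Each event must be documented with date of occurrence and duration, a changed resolution date makes a separate event, and subjects should be free of nausea, vertigo and dizziness before discharge. On that reading a Day 0 reaction and a Day 14 reaction are two records. Merging also needs severity, frequency and causality all to be consistent. This stands to the extent that merging is possible rather than certain. It does not remove the rule, and blinded raters with two causality categories may well judge both episodes alike.

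Other data are also collected. Side effects and vital parameters are recorded around each infusion, and "Any abnormal, clinically significant vital signs will be recorded as adverse events". SAFTEE-SI is completed after both infusions, and blood pressure, heart rate and ECG are separate safety assessments. These help, but none of them supplies TEAE incidence by treatment: SAFTEE-SI, for example, is listed and reported as percent change in its total score.

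A reader might infer three stronger things that the documents do not support:

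- *That drug-drug events are lost to nitroprusside.* By treatment these subjects remain counted; only Stage 2 entries and event counts can fall. Stage 2 placebo falls by the same mechanism.
- *That a repeated pre-treatment complaint is lost as a TEAE because of this rule.* This mostly fails. If severity or frequency rises, the merging condition is not met and section H counts the event. If neither rises, section H excludes an existing complaint whatever the intermittent rule says. What remains is the mismatch between section H (worsening counts) and section M and the SAP (onset only).
- *That the drug-placebo contrast always shrinks.* The Stage 2 difference does in these scenarios, but the Stage 2 ratio at correlation 0.8 is 0.149/0.044 = 3.4 against a true 3.0.

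**Conclusion.** The point holds as a gap in the recording and attribution rules. Two sites following the protocol can record the same facts differently, and under one reading a placebo-drug subject's nitroprusside reaction has no record. At pooled subject level that error runs only one way, towards a lower nitroprusside incidence.

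A reader might conclude that nitroprusside rates will be understated. The documents show only that they can be. At an assumed 30% and 10% per infusion, the pooled loss is 0 to 4.5 points, and Stage 2 nitroprusside reads between 30% (none merged) and 15% (all merged, correlation 0.8). These figures rest on assumed event rates, merge share and within-subject correlation, none of which is in the documents. The pooled effect is modest, but with 20 subjects per sequence one or two misfiled subjects are visible. The change should be made; the primary efficacy analysis is unaffected.

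**What to change.** 1. **Protocol section H, Timing, and the eCRF guidelines.** Limit the intermittent-event rule to recurrences within one period: pre-treatment, after the start of infusion 1, or after the start of infusion 2. An episode that starts after a new infusion begins is a new record with its own onset date, even if severity, frequency and causality are unchanged. Define consistent, and state how the rule fits with the sentence on resolution dates.
2. **Protocol section M and SAP, Adverse Events.** Count a subject once per preferred term within each stage, under the treatment infused in that stage, and state the denominators by stage.
3. **TEAE definition.** Use one definition, reconciling section H (worsening counts) with section M and the SAP (onset only).

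The cost is a few sentences, some additional adverse event lines and possibly slightly higher stated TEAE rates. If sites would never have merged across infusions, the first change alters no data.

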Nitroprusside infusion has been widely used for decades to control profound hypertension and most recent reviews have concluded that it is quite safe at doses less than 2 $\mu\text{g}/\text{kg}/\text{min}$. The most important adverse reactions to sodium nitroprusside are the avoidable ones of excessive hypotension and cyanide toxicity. (Package Insert <http://medlibrary.org/lib/rx/meds/nitropress/> - last revised January 16, 2014).

No adverse effects were observed in 10 schizophrenia subjects who received nitroprusside 0.5 $\mu\text{g}/\text{kg}/\text{min}$ in the study by Hallak et al., including no cases of hypotension despite administering nitroprusside to two subjects treated with chlorpromazine (500 mg/d and 300 mg/d); chlorpromazine has the greatest propensity for orthostatic hypotension of any antipsychotic and subjects taking this drug will be excluded from the study. Nitroprusside was also added to high-dose ziprasidone (240 mg/d) and high dose risperidone (8 mg/d) without measurable effects on blood pressure or EKG.

The potential for cyanide toxicity is greatest when more than 500 $\mu\text{g}/\text{kg}$ of sodium nitroprusside is administered faster than 2 $\mu\text{g}/\text{kg}/\text{min}$, as cyanide is generated faster than the unaided patient can eliminate it. Cyanide toxicity will be avoided in this study as the dose administered is very low, and individuals with renal disease will be excluded. Also, the study treatment will be infused within 3 hours of preparation as sodium nitroprusside is stable in solution for 24 hours.

Subjects will be continuously monitored for adverse effects during the infusion and blood pressure and heart rate will be taken and recorded 2 hours post infusion.

Given that subjects with renal disease, a history of orthostatic hypotension or medications that destabilize blood pressure will be excluded from the study, and that the infusion rate of SNP for subjects randomized to active drug in this study will be very low (0.5 $\mu\text{g}/\text{kg}/\text{min}$), the risk of excessive hypotension and cyanide toxicity is very low.

H. STUDY ASSESSMENTS – PLAN AND METHODS

Study Conduct

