In the event of a SAE, the PI or designate will notify the MGH-CTNI Medical Monitor by phone or email within 24 hours of the event and will email supporting documentation

within 48 hours of the event and then as relevant data is available within the following week.

The PI must inform the IRB immediately regarding any AE (does not have to be causally related) that is both serious and unexpected; or that represents a series of AEs that, on analysis, is unanticipated, or occurs at an unanticipated frequency, or otherwise represents an unanticipated safety risk to the study subject. The IRB may subsequently choose to modify the informed consent or request changes to the protocol.

Treatment-Emergent Adverse Events

A treatment emergent adverse event (TEAE) is an AE that either began following initiation of study treatment or was present prior to the initiation of the treatment, but increased in frequency or severity following initiation treatment, regardless of causality.

All TEAEs (post infusion) will be captured on the subject source documents for all required assessments and data transferred to the eCRF. The reporting PI or medically qualified Sub-Investigator will sign and date the source document and eCRF.

Procedures and follow-up of Subjects Experiencing AEs after Completion of or Withdrawal from the Study

If a subject experiences the onset of a SAE within a period of 30 days following study completion and, in the opinion of the PI or medically qualified Sub-Investigator, it is associated with the study, it will be followed up and reported as described above.

Protocol Waivers and Violations

Protocol Waivers

Protocol waivers will be assessed on a case by case basis by the medical monitor and the principle investigator for this study.

Procedure for Non-Compliant Subjects

Subjects who miss a study visit will be allowed (at the discretion of the PI) to make up that visit the next day. Subjects who miss more than one visit will be discontinued from the study. Subjects who withdraw consent will no longer have data collected for the study. Every effort will be made to maintain contact with patients who are discontinued, but who do not withdraw consent, according to the study schedule for 30 days post-treatment in order to collect safety data.

Protocol Deviation and Violation Definitions

Protocol violations as defined in the table below will be reported as described in the Manual of Operations.

Table 3. Major and Minor Protocol Violations

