No members of the study team at study sites, will have access to the randomization scheme during the conduct of the study, with the exception of the Site's unblinded pharmacist or nurse as designated by the PI.

The randomization schedule for blinding of randomized treatment will be maintained by MGH CTNI or representative and will not be disclosed until after database lock.

During the infusion visits, the study staff conducting the clinical efficacy assessments must not be able to view the bag containing the infusion solution to ensure that they remain blinded. The bag must be protected from view with an opaque covering.

Methods for Unblinding the Study

Individual treatment codes, indicating the treatment randomization for each randomized patient, will be available to the investigator(s) or pharmacists from MGH CTNI or its designee.

The treatment code must not be broken except in medical emergencies when the appropriate management of the patient necessitates knowledge of the treatment randomization. The investigator documents and reports the action to MGH CTNI or representative, without revealing the treatment given to the patient to MGH CTNI or representative's staff.

MGH CTNI retains the right to break the code for serious adverse events (SAEs) that are unexpected and are suspected to be causally related to a study drug and that potentially require expedited reporting to regulatory authorities. Treatment codes will not be broken

for the planned analyses of data until all decisions on the evaluability of the data from each individual patient have been made and documented.

J. ETHICAL CONSIDERATIONS

Risk/Benefit Assessment

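### The definition of an unexpected AE joins nature and severity with *and*, so a listed reaction worse than labelled can stay expected; separately, the SAE deadlines run from two different starting points

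*Protocol*

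**What the plan says.** **Definition.** Protocol section H, Expectedness: "An unexpected AE is any AE, the nature and severity of which is not consistent with the applicable product information". The reference document is given by example: "e.g., Package Insert of product characteristics for an approved product".

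**Rules that use the term.**
- Section H, Reporting Serious Adverse Events: "The PI must inform the IRB immediately regarding any AE (does not have to be causally related) that is both serious and unexpected". The same sentence goes on to cover a series of AEs that proves unanticipated, an unanticipated frequency, and any other unanticipated risk to the subject.
- Section I, Methods for Unblinding the Study: "MGH CTNI retains the right to break the code for serious adverse events (SAEs) that are unexpected". This right is further limited to SAEs suspected to be caused by a study drug and potentially subject to expedited regulatory reporting.

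**SAE deadlines.** Section H, Reporting Serious Adverse Events, first says: "All SAEs will be reported to MGH-CTNI by the PI through telephone or email within 24 hours of discovery". It then says that the PI or designate "will notify the MGH-CTNI Medical Monitor by phone or email within 24 hours of the event", with supporting documents due within 48 hours, also counted from the event.

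**The concern.** An expectedness rule should flag an event if it is new in kind or if it is worse than the reference information describes. With *and*, the second test no longer works alone: a known reaction in an unusually severe form passes as expected, although that is one of the signals the rule is meant to find.

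The protocol itself says that the IRB may respond to a notice by changing the consent form or asking for protocol changes. Section L describes a medical monitor designated by the coordinating center and mentions no data monitoring board, and section M plans no interim analysis. As far as the documents show, the IRB is the main outside check on emerging harm, so its trigger should not turn on how one conjunction is read.

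The deadline is a separate matter. A limit counted from the event can expire before the site knows that the event has happened. Sites would then be in breach through no fault of their own, or would each settle on their own reading.

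**Working it through.** The plan gives no figure to reproduce here. The check has three steps.

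**1. The definition under each conjunction.** Inputs: the Expectedness text, and two yes/no questions about an event.

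| Nature consistent with product information? | Severity consistent? | Unexpected under *and* | Unexpected under *or* |
|---|---|---|---|
| Yes | Yes | No | No |
| Yes | No | **No** | **Yes** |
| No | Yes | **No** | **Yes** |
| No | No | Yes | Yes |

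Under *and*, 1 of 4 combinations is unexpected; under *or*, 3 of 4. Two rows change. The second is the one at issue: a listed reaction that is worse than labelled. The first row does not change, so an event of listed type and listed severity stays expected either way.

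**2. Which escalation routes depend on the definition.**

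| Route | Where | Uses the definition? | What limits it |
|---|---|---|---|
| Immediate IRB notice: serious and unexpected | H, Reporting SAEs | Yes | The definition itself |
| Immediate IRB notice: unanticipated series, frequency or risk | H, Reporting SAEs | No | No definition of unanticipated and no reference rate |
| Medical monitor to PI to IRB, for safety concerns | I, Dose Modification | No | Judgement; the monitor gets the data within 24 hours of each infusion, but the IRB step has no time limit |
| All SAEs to the center and its medical monitor | H, Reporting SAEs | No | Does not itself reach the IRB |
| Unreported SAE is a major violation | H, Table 3 | No | Says IRB and/or center; sets no IRB deadline |
| Monitor reviews all AEs and works with the IRB on signals | L, Medical Monitoring | No | No timing |
| Center's right to break the code | I, Methods for Unblinding | Yes | Discretionary; also needs suspected causality and potential expedited reporting |
| Emergency unblinding | I; also Blinding in protocol section M and the SAP | No | In section I, tied to managing the individual patient |

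Two of the eight routes depend on the wording. The other six do not.

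**3. The clocks.** Inputs: nominal visits on Days 0, 7, 13, 14, 21 and 28 (section F), and limits of 24 and 48 hours.
- Longest gap between visits: 7 days × 24 = 168 hours, for example Day 14 to Day 21.
- An SAE arising just after one visit and first reported at the next could be up to 168 hours old.
- The 24-hour limit from the event would have passed up to 168 − 24 = 144 hours earlier, and the 48-hour limit up to 168 − 48 = 120 hours earlier.
- Counted from discovery, both limits can be met.

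This assumes no contact between visits. Section H also applies the same reporting to study-associated SAEs with onset up to 30 days after completion, when no visits are scheduled, so the delay there could be longer.

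**The case against.** **The text does not say *only if both*.** It uses a singular verb, which can be read as treating nature and severity as one profile. On that reading an event much worse than labelled is already inconsistent, and the rule works as *or*. This is a fair reading, and it shows that the wording is ambiguous rather than plainly wrong. It does not make the wording safe: the literal reading is equally available, and one word removes the doubt.

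**Most routes do not use the definition.** This stands, and it keeps the gap small. A serious event that slips past the first limb of the IRB rule still reaches the coordinating center and its medical monitor within 24 hours, and may reach the IRB as an unanticipated risk or a safety concern. Emergency unblinding is untouched.

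**The two SAE deadlines name different recipients.** The first goes to the coordinating center and the second to its medical monitor. Both belong to one organization, however, and different recipients do not make a deadline counted from the event workable.

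**A stronger inference that the documents do not support.** The protocol, citing the Package Insert, says "The most important adverse reactions to sodium nitroprusside are the avoidable ones of excessive hypotension and cyanide toxicity". It also says "Cyanide toxicity will be avoided in this study as the dose administered is very low". A reader might conclude that serious hypotension or cyanide toxicity at this dose would be classed as expected and so escape IRB notice and code-break. That goes too far:
- The insert's severity wording is not in the documents, so nobody can say from them which events would exceed it.
- A serious cyanide event would contradict the protocol's own assurance, which makes it a clear candidate for the unanticipated-risk limb.
- Hypotension is planned for in the blood pressure monitoring and infusion rules of sections H and I. Low risk is not the same as not expected.
- The study rate is 0.5/2 = 25% of the 2 µg/kg/min level, and one infusion is 0.5 × 240 = 120 µg/kg, or 120/500 = 24% of the 500 µg/kg figure. Both thresholds concern cyanide; the protocol gives none for labelled hypotension. They do not show that the label describes events only at about four times this exposure.
- No adverse effects in 10 treated subjects leaves an upper 95% limit of 1 − 0.025^(1/10) = 30.8% for an event rate. That says nothing about whether reporting would fail. That trial was also the only prior one in a psychiatric population, not the only experience with the drug that the protocol cites.

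**Conclusion.** The point holds in a limited form. Read literally, the definition leaves a listed reaction that is worse than labelled outside two rules: the serious-and-unexpected limb of the IRB notice, and the coordinating center's discretionary code-break. The remaining routes reduce the gap without closing it, because they rely on undefined judgement, set no time for the IRB step, or serve another purpose.

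The clock conflict does not depend on interpretation. The two starting points differ, and a site cannot meet the one counted from the event when it learns of the SAE too late.

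The first conclusion assumes that some sites would apply the literal wording; the second assumes that some SAEs become known only later. The documents do not allow an estimate of how often either would occur. The matter concerns safety reporting only: no efficacy result, sample size or error rate is affected.

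**What to change.** 1. In section H, Expectedness, replace *nature and severity* with *nature or severity*.
2. In section H, Reporting Serious Adverse Events, count the 24-hour notice to the medical monitor and the 48-hour document deadline from discovery, as for the report to the coordinating center.
3. Reconcile Expectedness and Reporting Serious Adverse Events (section H) with Dose Modification during Treatment and Methods for Unblinding the Study (section I), so that the same serious events lead to IRB notice and to a review of whether to break the code. The causality condition on the code-break itself can remain.

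Declaring every SAE of hypotension or cyanide toxicity unexpected, or replacing the label as the reference, would be a larger and debatable choice. Neither is needed for this correction.

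The cost is a few sentences and, as a judgement rather than a calculation, perhaps one or two additional expedited reports.
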